8.2 EVALUATION OF SPONTANEOUS EVENTS

Since implant passing and adverse events are spontaneous, such events may not align with study data collection. As such data collection is prepared for unscheduled follow-up visits; reporting and evaluation of implant passing and adverse events will be explicitly requested at all follow-up timepoints.

8.3 ADVERSE EVENTS AND SERIOUS ADVERSE EVENTS

8.3.1 DEFINITION OF ADVERSE EVENTS (AE)

Adverse event means any untoward medical occurrence associated with the use of an intervention in humans, whether or not considered intervention-related (21 CFR 312.32 (a)).

Adverse Event details will be classified and reported by a study investigator and confirmed by the study PI. Classifications of adverse events are described below. Clip passing, by itself, is *not* an adverse event.

8.3.2 DEFINITION OF SERIOUS ADVERSE EVENTS (SAE)

An adverse event (AE) or suspected adverse reaction is considered "serious" if, in the view of either the investigator or sponsor, it results in any of the following outcomes: death, a life-threatening adverse event, inpatient hospitalization or prolongation of existing hospitalization, a persistent or significant incapacity or substantial disruption of the ability to conduct normal life functions, or a congenital anomaly/birth defect. Important medical events that may not result in death, be life-threatening, or require hospitalization may be considered serious when, based upon appropriate medical judgment, they may jeopardize the participant and may require medical or surgical intervention to prevent one of

the outcomes listed in this definition. Examples of such medical events include allergic bronchospasm requiring intensive treatment in an emergency room or at home, blood dyscrasias or convulsions that do not result in inpatient hospitalization, or the development of drug dependency or drug abuse.

8.3.3 CLASSIFICATION OF AN ADVERSE EVENT

Adverse events will be coded using a validated medical dictionary (MedDRA - Medical Dictionary for Regulatory Activities, (McLean, VA)).

SEVERITY OF EVENT

The following guidelines will be used to describe the severity of an adverse event.

- Mild Events require minimal or no treatment and do not interfere with the participant's daily activities.
- **Moderate** Events result in a low level of inconvenience or concern with the therapeutic measures. Moderate events may cause some interference with functioning.
- **Severe** Events interrupt a participant's usual daily activity and may require systemic drug therapy or other treatment. Severe events are usually potentially life-threatening or incapacitating. Of note, the term "severe" does not necessarily equate to "serious".

RELATIONSHIP TO STUDY INTERVENTION

The clinician's assessment of an AE's relationship to study intervention (Zip-stitch™ system or VICRYL™) is part of the documentation process, but it is not a factor in determining what is or is not reported in the study. If there is any doubt whether a clinical observation is an AE, the event should be reported. All AEs must have their relationship to study agent assessed. For all collected AEs, the clinician who examines and evaluates subjects will determine the AE's likely causality based on temporal relationship and his/her clinical judgment. The causality will be graded using the categories below:

- **Definitely Related** There is clear evidence to suggest a causal relationship, and other possible contributing factors can be ruled out. The clinical event, including an abnormal laboratory test result, occurs in a plausible time relationship to study intervention administration and cannot be explained by concurrent disease or other drugs or chemicals. The response to withdrawal of the study intervention should be clinically plausible.
- Probably Related There is evidence to suggest a causal relationship, and the influence of other
 factors is unlikely. The clinical event, including an abnormal laboratory test result, occurs within
 a reasonable time after administration of the study intervention, is unlikely to be attributed to
 concurrent disease or other drugs or chemicals, and follows a clinically reasonable response on
 withdrawal.
- Potentially Related There is some evidence to suggest a causal relationship (e.g., the event occurred within a reasonable time after administration of the trial medication). However, other factors may have contributed to the event (e.g., the participant's clinical condition, other concomitant events). Although an AE may rate only as "possibly related" soon after discovery, it can be flagged as requiring more information and later be upgraded to "probably related" or "definitely related", as appropriate.
- **Unlikely to be related** A clinical event, including an abnormal laboratory test result, whose temporal relationship to study intervention administration makes a causal relationship improbable (e.g., the event did not occur within a reasonable time after administration of the

- study intervention) and in which other drugs or chemicals or underlying disease provides plausible explanations (e.g., the participant's clinical condition, other concomitant treatments).
- Not Related The AE is completely independent of study intervention administration, and/or
 evidence exists that the event is definitely related to another etiology. There must be an
 alternative, definitive etiology documented by the clinician.

OUTCOME OF EVENT

The following guidelines will be used to categorize and describe the outcome of an adverse event:

- Fatal Event has caused patient death.
- Ongoing, not improving Subject has not recovered and is not improving since initial reporting
 of event.
- Ongoing, improving Subject has not recovered, but is improving since initial reporting of event.
- Recovered w/ sequelae Subject has recovered from event, but with complications.
- Resolved Subject has completely recovered from event, with no complications.

TREATMENT OF EVENT

The following guidelines will be used to categorize and describe the treatment of an adverse event:

- None Subject was administered no treatment for the event.
- Medication(s) Subject was prescribed medication to treat the event. Medication, including
 dosing, should be recorded in the Concomitant Medications/Therapies portion of Adverse event
 log.
- Non-medication Subject was administered some treatment or therapy other than medication in effort to address the event. This includes outpatient treatment only.
- Hospitalization Subject was admitted to the hospital for treatment of this event.
- Other Another type of treatment was administered, to be described in the Adverse Event Log.

EXPECTEDNESS

An AE will be considered unexpected if the nature, severity, or frequency of the event is not consistent with the risk information previously described for the study agent in Section 2. In other words, expectedness is binary and will be recorded as Yes or No in an Adverse Event Log as determined by the PI according to identified risks.

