7 PARTICIPANT DISCONTINUATION, WITHDRAWAL, AND LOSS TO FOLLOWUP

7.1 DISCONTINUATION OF STUDY INTERVENTION

As this study involves a single surgical treatment, discontinuation from study test intervention occurs in the circumstance of an additional procedure required to address failed cuff closure, or dehiscence. In this case, cuff closure with the test or reference article will have failed and will be reflected in cuff closure failure rate reported the secondary study endpoint analysis. If a subject receives an additional procedure to address vaginal cuff dehiscence, they will re-start study follow-up, including one week, six week, and six month in-person visits and a 12-month phone call. All secondary endpoint data collection will be re-performed according to the new follow-up schedule and will be included in secondary endpoint analysis.

In any circumstance in which an investigator determines it necessary to discontinue subject participation for reasons other than vaginal cuff dehiscence, that subject will be discontinued from the study and may not be included in study analysis. The reason(s) for discontinuation will be documented on the End of Study CRF.

Overall study discontinuation and closure is further discussed in section 10.1.2.

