8.3.4 TIME PERIOD AND FREQUENCY FOR EVENT ASSESSMENT AND FOLLOW-UP

Any medical condition that is present at the time that the subject is screened, but does not exclude said subject, will be considered as baseline and not reported as an AE. However, if the study subject's condition deteriorates at any time during the study, it will be recorded as an AE.

Changes in the severity of an AE will be documented to allow an assessment of the duration of the event at each level of severity to be performed. AEs characterized by surgeon to be intermittent, or having distinct episodes, require documentation of onset and duration of each episode.

An investigator will record all reportable events with start dates occurring any time after informed consent is obtained until the last day of study participation, AEs occurring before, but not resolving by, the last day of study participation will be followed for an additional 7 (for non-serious AEs) or 30 days

Protocol QD-PRO-045 Rev 005

(for SAEs) after. If such an SAE is determined to be probably or definitely related to the investigational device, then it may be followed for longer.

At each study visit, the investigator will inquire about the occurrence of AE/SAEs since the last visit. Events will be followed for outcome information until resolution or stabilization. All AEs will be followed to adequate resolution.

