Secondary Endpoint (3) Comparison of implant passing rates.

Data collection: Implant passing rates will be calculated and the percentage of subjects experiencing one or more implant passing events will be compared between the test and control groups at six weeks and at six months.

Acceptance Criteria: Endpoint success is defined as a percentage of subjects experiencing implant passing in the test group less than or equal to that of the reference group.

Statistical Analysis Method: A two-sided Fisher's Exact Test will compare (test versus reference) percentage of subjects experiencing implant passing events between test and reference groups. Assessment of this is independent of the primary study endpoints.

Secondary Endpoint (4) Relationship of Implant passing to Adverse Events.

Data collection: Frequency of implant passing events associated with an Adverse Event will be evaluated through six-weeks post-operative. Associating implant passing to an Adverse Event will include consideration of temporal and possible causal relationship. The AE relatedness terms described in Section 8.3.3 will be utilized in determination of implant passing to a given Adverse Event, where "relatedness to study intervention" is replaced with "relatedness to implant passage." This will not replace determination of relatedness to the study device, which will be performed separately according to study safety reporting details. Adverse Events determined to be 'probably' or 'definitely' related to an implant passing event will be considered a per patient failure of the primary efficacy endpoint. Relationship of implant passing events to AEs will be reported independently and compared between test and control groups.

Acceptance Criteria: Endpoint success is defined as a percentage of subjects experiencing implant passing event related to an AE in the test group less than or equal to that of the reference group.

Statistical Analysis Method: A two-sided Fisher's Exact Test will compare (test versus reference) percentage of subjects experiencing implant passing event associated with an AE between test and reference groups. Assessment of this is independent of the primary study endpoints.

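### The two highest causality grades in 8.3.3 look for a response to withdrawal, which suits a drug better than an implanted closure and has no meaning for relatedness to implant passage in 9.4.4(4).

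*Combined protocol and SAP*

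**What the plan says.** **Causality scale (8.3.3).** The examining clinician judges "likely causality based on temporal relationship and his/her clinical judgment" and records the result in one of five categories.

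- *Definitely Related*: after the criteria on timing and alternative causes comes "The response to withdrawal of the study intervention should be clinically plausible".
- *Probably Related*: the event occurs within a reasonable time, is unlikely to have another cause, "and follows a clinically reasonable response on" withdrawal.
- *Potentially Related*: "There is some evidence to suggest a causal relationship". There is no withdrawal element. The example given refers to a trial medication.

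**Intervention (7.1).** The section begins "As this study involves a single surgical treatment", and the only discontinuation of treatment it describes is a further procedure for failed closure or dehiscence. The Synopsis puts clip absorption at five to eight months.

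**Secondary endpoint 4 (9.4.4).** The 8.3.3 terms are carried over, with implant passage replacing study intervention as the thing the event is related to. The sentence that sets a threshold covers "Adverse Events determined to be 'probably' or 'definitely' related to an implant passing event" and calls these per-patient failures of the *primary* efficacy endpoint. Evaluation runs through six weeks. Success means a test-group percentage no higher than the reference percentage.

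**Other definitions of the same endpoint.** Sections 3.2(4) and 10.2 define an associated event as one that is device-related and temporally related to the passing event. Neither sets a minimum grade.

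**The concern.** A response to withdrawal is informative for a drug that can be stopped. A clip or suture placed once and left to absorb is not stopped, so for most women there is nothing to observe within the window of endpoint 4. A rater who follows the categories to the letter cannot use *Probably Related* without that response, has a weaker obstacle at *Definitely Related*, and finds the next grade down free of it.

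The problem is sharper in 9.4.4(4). A passing event cannot be withdrawn, yet the grades with the withdrawal wording are the two that the section names as failures. Some raters will ignore the clause and others will apply it. Section 4.1 foresees two initial sites and at least three surgeons, so this is a source of inconsistent measurement. A low count for endpoint 4 could then reflect the wording of the scale as well as the behaviour of the device.

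**Working it through.** **1. The grades side by side (8.3.3).**

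| Grade | Withdrawal element | Force | Named as failure in 9.4.4(4) |
|---|---|---|---|
| Definitely | yes | expected (should be) | yes |
| Probably | yes | required (joined by *and*) | yes |
| Potentially | none | – | no |

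An event with clear timing and no other cause, but no withdrawal to assess, meets every element of *Probably Related* except the last. Read literally, it is graded *Potentially Related*.

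**2. Is there a withdrawal to observe?** Clip absorption (five to eight months) falls after the six-week window. The documents give no absorption time for the suture. Material can leave early by spontaneous passing, by removal by medical staff (both in 3.1) or at re-intervention (7.1). Section 2.2 intends four to five clips per woman, so others may remain after one passes. In 9.4.4(4) the event is related to the passage itself, so a clip leaving is the suspected cause and not its withdrawal.

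**3. Which grade counts for endpoint 4?** Sections 3.2(4) and 10.2 give no minimum. Section 9.4.4(4) gives *probably* or *definitely*, but attaches it to the primary efficacy endpoint. Section 3.1 defines failure of that endpoint as any spontaneous passing event, whatever its link to an adverse event. Section 3.2(4) refers to 9.4.2 for the detailed determination, and 9.4.2 sets no grading criteria. The passages conflict.

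**4. Size, for illustration.** The plan states no rate for endpoint 4. Its enrolment figure reproduces: 35 / 0.9 = 38.9, rounded up to 39 test; 39 / 2 = 19.5, rounded up to 20 reference; total 59. I assume 35 test and 20 × 0.9 = 18 reference women are evaluable.

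- One counted test event against none: 1/35 = 2.9% (exact 95% CI 0.1% to 14.9%) vs 0/18. The criterion is missed, although the two-sided Fisher p is 1.0.
- The same event downgraded: 0/35 vs 0/18. The criterion is met.

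The chance of at least one counted test event is 1 − (1 − p(1 − q))^35, where p is the true per-woman rate of passage-related adverse events and q the share downgraded. Both are assumptions:

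| p | q = 0 | q = 0.5 | q = 1 |
|---|---|---|---|
| 2% | 0.51 | 0.30 | 0 |
| 5% | 0.83 | 0.59 | 0 |
| 10% | 0.97 | 0.83 | 0 |

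For example, with p = 5% and q = 0.5: 1 − 0.975^35 = 0.59. The documents do not allow q to be estimated.

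**The case against.** The case for leaving the scale alone has real content.

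- **Clinical judgment governs.** Section 8.3.3 rests causality on timing and judgment, the *Definitely* clause is soft, grades may be upgraded later, and 10.1.5 provides independent adjudication of safety events. This stands against any claim that events *will* be downgraded. It does not remove the risk: a category must still be chosen, the upgrade leads to grades with the same wording, and the adjudicator is given no other scale.
- **Withdrawal can happen.** A reader might infer that it can never be observed. The documents do not support that: endpoint 4 concerns women who have passed at least part of an implant, and removal and re-intervention are also mentioned. What stands is that withdrawal is not available for most women and is not defined for relatedness to passage.
- **The threshold is not settled.** Under 3.2(4) and 10.2 an event graded *Potentially Related* could still count, which would shrink the effect on endpoint 4. This stands, and it is a reason to reconcile the passages.
- **Other safety outputs are largely protected.** A reader might infer that related events vanish from the adverse event comparison or lose follow-up. Section 8.3.3 says relatedness does not decide what is reported, and 9.4.5 tabulates all events with no minimum grade and no acceptance criterion. Sections 8.3.4 and 8.3.6 follow events to resolution or stability whatever the grade. The clause beginning "If such an SAE is determined to be probably or definitely related to the investigational device" only permits longer follow-up.
- **Impact is limited.** The Synopsis labels the secondary endpoints exploratory, and 9.2 says they are not powered.

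**Conclusion.** The wording problem is real and worth correcting. *Probably Related* requires, and *Definitely Related* expects, a withdrawal response that most women with a one-time implanted closure will not have within six weeks, and that has no meaning for relatedness to implant passage. Followed literally, the scale can move an event below the threshold in 9.4.4(4). With the assumed 35 and 18 evaluable women, a single such move can reverse the result for endpoint 4.

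The documents go no further. They do not show how often downgrading would occur. The scale applies to both arms, so no direction of between-arm bias follows. The primary efficacy result as defined in 3.1 does not depend on any adverse event grade.

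A reader might take the earlier clinical testing in 2.3.4 as evidence, since its six device-attributed events (1 scar infection + 2 urinary tract infections + 3 vaginal bleeding) were all called possibly related. That inference fails: the scale used there is not described, and such events after hysterectomy have evident competing causes.

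**What to change.** 1. **8.3.3:** delete the withdrawal clauses from the top two grades, or apply them only when the implant was removed or passed. Replace the reference to trial medication with study device. Do not add a required location criterion: 2.3.2 lists bladder erosion from a misplaced clip as a risk, and such a rule could itself downgrade device events away from the cuff.
2. **9.4.4(4):** grade passage-relatedness on timing to the passing event and absence of another cause, with no withdrawal element.
3. **Reconcile 9.4.4(4) with 3.2(4) and 10.2:** state one minimum grade that counts for endpoint 4, and point 3.2(4) to the section that holds the criteria.
4. **9.4.4(4):** correct the statement that these events are failures of the primary efficacy endpoint, which conflicts with 3.1.

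The cost is wording in a few sections and matching guidance on the adverse event form. No data collection or sample size changes. The downside is that more events may be graded as device- or passage-related.

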2.3.4 ASSESSMENT OF POTENTIAL RISKS AND BENEFITS

A risk analysis of the Zip-stitch[™] System has been conducted in compliance with CFR 820/ISO 14971. All potential risks have been mitigated through appropriate System design controls and confirmed by preclinical bench and/or laboratory testing. The results of the analysis indicate that all potential device-related hazards have been reduced to an acceptable level. The Zip-stitch[™] System materials have been shown to be biocompatible and acceptable for human use.

No major adverse events (AEs) were reported when it was used in a similar population. However, in previous clinical testing reported adverse events include four reported fevers and one case of herpes zoster, all unrelated to Zip-stitch™. Adverse events "possibly related" to the device were one umbilical scar infection, two urinary tract infections, and three cases of post-operative vaginal bleeding. There was also one case of granuloma of the vaginal vault reported at six months. Reported pain continued to decrease over the course of the observed 12-month extension period and was consistent with expectations for this study population. Furthermore, reported dyspareunia was both mild and infrequent, consistent with published literature.

While the benefits of the Zip-stitch[™] have not been well characterized (this characterization is part of the purpose of this trial), clinical evaluation reports suggest that the device may be faster and easier to learn and use than the existing standard of care. Additionally, clinical evaluation has noted the added benefit of no sharps hazard.

Risks identified via the device's risk analysis will be mitigated both at the patient level and at the study/population level. The protocol describes safety related stopping rules in Section 10.1.2.

All of the medical risks identified above are risks typically associated with laparoscopic hysterectomy. Based on existing preclinical and clinical data, there is no reason to believe these concerns will be heightened by use of the Zip-stitch™ system.

Separate from surgery, there is possible social/financial risk associated with study participation, due to the possibility of more travel/visits needed to satisfy follow-up than would otherwise be required. The sponsor will provide nominal renumeration for time and travel consistent with what would normally be required to mitigate this risk.

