9.4.5 ANALYSIS OF SECONDARY SAFETY ENDPOINTS

The Safety population will be the analysis population for all safety analyses.

Secondary Endpoint (5) Comparison of incidence of adverse events.

Data collection: Adverse Events will be tabulated for both the test and reference groups. All AEs and SAEs will be MedDRA-coded and summarized by treatment arm. In addition, the number and proportion of AEs and SAEs will be calculated for each group. For each MedDRA-coded medical term, the proportion of subjects who experience at least one of the following will be reported and compared.

Adverse event

- Adverse event related to treatment
- Serious adverse event
- Serious adverse event related to treatment
- Adverse event leading to study discontinuation
- Serious adverse event leading to study discontinuation

Classification of AEs will also be presented and compared. Events will be reported by MedDRA system organ class and preferred term. Adverse Events will be compared by severity and device relatedness between the test and reference groups.

Acceptance Criteria: There is no defined endpoint acceptance criteria for the comparison of adverse events.

Statistical Analysis Method: A two-sided Fisher's Exact Test will compare (test versus reference) rate of incidence of adverse events by six months post-operative. Assessment of this is independent of the primary study endpoints.

Secondary Endpoint (6) Comparison (test to reference group) of non-increase in subject dyspareunia scores from baseline to 6-months post-operative.

Data collection: Individual subject dyspareunia will be assessed using the relevant sexual discomfort module of the validated Female Sexual Function Index (FSFI). Higher scores indicate good sexual function with little or no sexual discomfort, and lower scores indicate poor sexual function with higher levels of sexual discomfort. Scores of zero indicate no sexual activity and will not be included in comparison of non-increase in dyspareunia.

Acceptance Criteria: A subject level failure is defined as a decrease in sexual function score (signifying an increase in dyspareunia). Endpoint success is defined as the same or lower rate of FSFI score decrease in the test group at six months when compared to the reference group at six months.

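### The AE causality scale has no item for the hysterectomy and its 'Unlikely' grade is closed to early post-operative events, so the related-AE comparison is diluted if 'Potentially Related' counts as related, which the plan leaves open

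*Combined protocol and SAP*

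**What the plan says.** Section 8.3.3 (Relationship to Study Intervention) uses one five-level scale. What is graded is the "relationship to study intervention (Zip-stitch™ system or VICRYL™"); the hysterectomy, access and anaesthesia are not named as something to grade. The examining clinician "will determine the AE's likely causality based on temporal relationship and his/her clinical judgment".

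The three lower grades are:

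- *Potentially Related* needs some evidence of causality. The example given is that "the event occurred within a reasonable time after administration of the trial medication". Other contributing factors are allowed for and do not lower the grade.
- *Unlikely* needs an event "whose temporal relationship to study intervention administration makes a causal relationship improbable" "and in which other drugs or chemicals or underlying disease provides plausible explanations". The closing examples also mention concomitant treatments.
- *Not Related* needs complete independence from the intervention or a definite other cause, and the clinician must document a definitive alternative etiology.

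Section 9.4.5, endpoint 5, lists "Adverse event related to treatment" and the SAE equivalent among the proportions to be compared between arms, and compares AEs by device relatedness. It does not say which grades make an event related. Section 10.2 also uses the 8.3.3 grade to define an associated AE, which feeds secondary endpoint 4.

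Section 2.3.4 reports that in earlier testing the events rated possibly related to the device "were one umbilical scar infection, two urinary tract infections, and three cases of post-operative vaginal bleeding".

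**The concern.** Under Section 8.1, cuff closure follows uterine excision within one operation. An event in the first days after surgery therefore has much the same time relation to the device as to the hysterectomy. A scale that grades only the device, and that needs improbable timing before a clinician may choose *Unlikely*, gives no natural place to an ordinary surgical complication whose cause is likely but not proven.

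What is at stake is how the treatment-related AE and SAE rates read. Section 2.3.1 calls infection and bleeding common after hysterectomy. If such events enter the related-AE rates, those rates move towards the all-AE rates in both arms. They then say less about the device, which is the reason for tabulating them separately. With 59 women and no powered safety comparison, readers will rely on these descriptive rates.

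**Working it through.** **1. Reading the scale for one case.** Take an early post-operative infection that the clinician thinks is probably due to the surgery, without proof.

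- *Not Related*: unavailable, because there is no definitive etiology to document.
- *Unlikely*, alternative explanation: arguably met. Surgery is not a drug, a chemical or underlying disease, but the examples include concomitant treatments and a hysterectomy can be read into that.
- *Unlikely*, timing: not met. The two conditions are joined by 'and', so this alone closes the grade.
- *Potentially Related*: met, since timing is the example of sufficient evidence and other contributing factors are allowed.

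**2. Does the grade reach the analysis?** It does in 9.4.5, endpoint 5, but the cut-off is undefined. The only cut-offs in the plan are probably/definitely, in 8.3.4 for extended SAE follow-up and in 9.4.4, endpoint 4, for relation to implant passing. If endpoint 5 used that cut-off, most of these events would drop out of the related count.

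**3. Denominators.** The plan's goal is 35 test subjects with 10% loss: 35/0.9 = 38.9, so 39 test; 39/2 = 19.5, so 20 reference; total 59. This reproduces the planned enrolment.

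**4. Effect if *Potentially Related* counts.** The documents give no AE or related-AE rates, so all rates here are assumptions. Let d be the proportion of women with a truly device-related AE and h the proportion with a hysterectomy event graded as related, equal in both arms and independent of d. The observed proportion is p = 1 − (1 − d)(1 − h). For example, d = 0.40 and h = 0.20 give 1 − 0.60 × 0.80 = 0.52. Power is exact for the two-sided Fisher test at 0.05, 39 v 20.

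| True d, test v reference | h | Observed p | Risk ratio | Power |
|---|---|---|---|---|
| 40% v 10% | 0 | 40% v 10% | 4.0 | 65% |
| 40% v 10% | 20% | 52% v 28% | 1.9 | 35% |
| 40% v 10% | 30% | 58% v 37% | 1.6 | 26% |
| 30% v 5% | 0 | 30% v 5% | 6.0 | 62% |
| 30% v 5% | 20% | 44% v 24% | 1.8 | 27% |
| 20% v 10% | 0 | 20% v 10% | 2.0 | 10.5% |
| 10% v 10% | 0 | 10% v 10% | 1.0 | 2.7% |
| 10% v 10% | 40% | 46% v 46% | 1.0 | 3.2% |

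The contrast shrinks and the absolute rates rise. With no true difference the rejection rate stays between 2.7% and 3.6% for h from 0 to 40%, so no spurious difference appears. The 20% v 10% row shows that for smaller true differences the sample size already removes nearly all power.

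**5. What the earlier study adds.** Section 2.3.4 lists six possibly related events, of which one (the umbilical scar infection) is clearly remote from the cuff. The two urinary infections are less clear, because 2.3.2 names clip impingement on the bladder as a device risk. The same section reports four fevers and a herpes zoster as unrelated, and does not say which scale was used. This history is suggestive only and gives no usable estimate of h.

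**The case against.** The strongest reply is that the scale is not mechanical. Causality rests on timing and clinical judgment together, timing is only an example under *Potentially Related*, and a sensible clinician would grade an obvious surgical complication low. In addition:

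- The independent medical monitor (10.1.5) judges test-article relatedness for serious or unexpected events and adjudicates all safety events.
- Randomisation spreads hysterectomy events over both arms.
- The all-AE and all-SAE comparisons do not use the grade.
- AEs are also summarised by relatedness, so a pile-up in *Potentially Related* could be seen.
- Endpoint 5 has no acceptance criterion, and 4.2 and 9.2 say that secondary endpoints are not powered.
- Over-attribution to a new device is cautious.

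Much of this stands and limits the size of the point. It does not remove it. Judgment exercised against the written definition of *Unlikely* will vary between clinicians and sites. Infection and bleeding are listed in Section 2, so ordinary non-serious cases are probably expected events and miss the monitor's relatedness trigger; the general adjudication role has no procedure item to work with. Over-attribution is cautious for the absolute rate, but it works against detecting a difference between arms.

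A reader might infer three stronger things that the documents do not support. First, that the scale biases the comparison against Zip-stitch: both arms are graded the same way and both are inflated. Second, that 2.3.4 shows this scale misgrading events: the scale used there is not stated, and other events were graded unrelated. Third, that no early event can fall below *Potentially Related*: *Not Related* is open at any timing with a documented definitive cause.

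**Conclusion.** The point holds as a gap in the grading rule with a conditional consequence. There is no procedure-relatedness item, and the timing condition closes *Unlikely* to early events, so a probable but unproven hysterectomy complication is literally *Potentially Related*. Whether this reaches the related-AE comparison depends on a cut-off that 9.4.5 does not set.

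If *Potentially Related* counts, absolute device-related rates are inflated in both arms and the contrast is diluted. Under an assumed 40% v 10% the risk ratio falls from 4.0 to between 1.9 and 1.6, and power from 65% to between 35% and 26%, for assumed backgrounds of 20% to 30%. With a probably/definitely cut-off, most of the effect disappears. These sizes are illustrations and not estimates, because the documents give no rates. Secondary endpoint 4 is also touched, since an associated AE must be device-related under 8.3.3. The primary endpoints and the all-AE comparisons are unaffected.

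The change is worth making because it is cheap and because the related-AE rates will be read descriptively.

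**What to change.** 1. In 8.3.3 and on the AE form, record two separate items with the same five grades: relation to the closure device, and relation to the hysterectomy procedure (access, anaesthesia, catheter, uterine removal).
2. Reword *Unlikely* so that a more plausible alternative cause, including the surgery, is enough without improbable timing.
3. In 9.4.5, endpoint 5, base treatment-related AEs and SAEs on the device item, state which grades count as related, and tabulate the procedure item alongside. Use the same definition of device-related for associated AEs in 3.2(4) and 10.2.
4. Have the medical monitor's review under 10.1.5 use the same two items.

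While editing, use one name for the middle grade, which 8.3.3 calls both potentially and possibly related, and reconcile 2.3.1 (no infection observed in testing) with 2.3.4 (infections listed).

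The cost is one added field on the AE form, wording changes in the sections named, and a small amount of extra tabulation. The sample size and the primary analysis do not change.
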